9. RESEARCH METHODS

9.1. Study design

This study is a non-interventional, retrospective, evaluational study based on data extracted and analyzed from the RCC Registry.

This study was designed to answer the Sunitinib treatment responses/objective response rate according to disease risk group in patients with mRCC.

PFIZER CONFIDENTIAL

9.2. Setting

Analysis for this study will be conducted on data anonymized and extracted from RCC Registry; time frame for this study data set is information of eligible patients that were registered in RCC Registry between March 2019 and October 2022.

RCC Registry is a data log where clinical information is recorded by inviting patients who meet the patient selection criteria according to registry protocol from 6 different centers since March 2019. In this study, RCC Registry will be used as sole data source.

The annual disease burden in contributing centers to RCC Registry is approximately 100 patient/center, the treatment of an average of 250 patients per year is continued in the centers. Therefore, it is estimated that information of approximately 400 eligible patients who were registered in RCC Registry from 2019 to 2022 will be included in the analysis.

Study Schedule GES / Timeline	November 2022	December 2022	January 2023	February 2023	March 2023	April 2023
Preparation phase and obtaining necessary approvals	X	X				
Extracting data from RCC Registry			X	X		
Data management, statistical analysis and reporting				X	X	X

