9.2.1. Inclusion criteria

Data record in registry must meet all of the following inclusion criteria to be eligible for inclusion in the study:

1. Being a Turkish citizen
2. Being older than 18 years-old

3. Being clinically diagnosed and treated with mRCC
4. Being treated with Sunitinib in first line

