9.3. Variables

The following variables will be extracted from RCC Registry in the scope of this study:

- Demographic information (age, sex)
- Physical measurements (height and weight measurements)
- Disease and concomitant disease history (Hypertension, Diabetes mellitus)
- Previous treatments (ACE-I / ARB, statin)
- Age of start of Sunitinib,
- Smoking history,
- Date of diagnosis
- Surgery type (Radical nephrectomy, partial nephrectomy)
- Histopathological information
 - Pathological type,
 - Pathological stage and location,
 - T size and location
 - Fuhrman Grade,
 - Adrenal involvement,
 - Lymph node (LN) involvement,
 - Number of LNs removed,
 - Sarcomatoid feature,

- Other involvement information
- Treatment given (order of treatment given, starting date, dose, dose changes, if available)
- Discontinuation of treatment information and the reason
- Previous IFN use
- Toxicities leading dose reduction and treatment discontinuation
- Information of risk (International Metastatic RCC Database Consortium (IMDC), Memorial Sloan Kettering Cancer Center (MSKCC) subgroups)
- Performance scores (ECOG)
- Metastasis site information
- Laboratory values, if available
- Survival status

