9.5. Study size

In the scope of the study, RCC Registry will be screened for all patients who meets all inclusion criteria and who doesn't meet the exclusion criterion defined in the study protocol and who were treated with Sunitinib in first-line therapy for mRCC and were registered to the database between 2019 and 2022.

The annual disease burden in contributing centers to RCC Registry is approximately 100 patient/center, the treatment of an average of 250 patients per year is continued in the centers. Therefore, it is planned to include the information of approximately 400 patients whom records were registered in between 2019 and 2022 and who meet the patient selection criteria.

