9.6. Data management

The below data in Registry database will be anonymized by registry administrators.

- Variables to be obtained from the Registry : Demographic information (age, sex), physical measurements (height and weight measurements), disease and concomitant disease history (Hypertension, Diabetes mellitus), previous treatments (ACE-I / ARB, statin), age of start of Sunitinib, smoking history, date of diagnosis, surgery type (Radical nephrectomy, partial nephrectomy), histopathological information and other involvement information, treatment given (order of treatment given, starting date, dose, dose changes, if available), discontinuation of treatment information and the reason, previous IFN use, toxicities leading dose reduction and treatment discontinuation, information of risk (IMDC, MSKCC subgroups), performance scores, metastasis site information, laboratory values, if available, survival status .
- This anonymized data will be transferred to the clinical database of the study in Omega CRO.
- Omega CRO will analyze this anonymized data and provide the results to Pfizer.

No individual anonymized patient data will be provided to Pfizer.

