9.7. Data analysis

The Statistical Package for Social Sciences (SPSS) 19.0 for Windows will be used for the analysis. A type-I error of less than 5% will be interpreted as statistically significant.

Normality of data will be tested using the visual (histogram and probability plots) and analytical (Kolmogorov-Smirnov/Shapiro-Wilk tests) methods. Descriptive statistics will be expressed as numbers and percentages for categorical variables and as mean and standard deviation for normally distributed numerical variables, median and interquartile range (IQR) for non-normally distributed numerical variables. For Survival Analyses, Kaplan-Meier estimates will be calculated and for survival rate comparison of Kaplan-Meier estimates within selected categorical groups will be investigated using log rank test.

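### Cohort entry is by registration date and invitation, with no link to sunitinib start and no delayed entry in the Kaplan-Meier plan, so survival may be overstated

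*Combined protocol and SAP*

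**What the plan says.** Section 9.2 fixes the data set by date of registration: "eligible patients that were registered in RCC Registry between March 2019 and October 2022". It describes the registry as one in which "clinical information is recorded by inviting patients who meet the patient selection criteria according to registry protocol from 6 different centers since March 2019". Section 9.5 restates the cohort as patients "who were treated with Sunitinib in first-line therapy for mRCC and were registered to the database between 2019 and 2022"; the only date given there belongs to registration.

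The treatment criterion in 9.2.1 is simply "Being treated with Sunitinib in first line". It sets no window for the start of treatment and no maximum gap to registration. The single exclusion in 9.2.2 concerns patients lost to follow-up after starting treatment and does not limit that gap.

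Survival is a secondary objective (section 8). Section 9.7 says that Kaplan-Meier estimates will be calculated and that "for survival rate comparison of Kaplan-Meier estimates within selected categorical groups will be investigated using log rank test". It states no time origin, event, censoring rule or delayed entry.

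For timing, 9.3 lists date of diagnosis and "Treatment given (order of treatment given, starting date, dose, dose changes, if available"; the closing qualifier may also apply to the starting date. The list in 9.6 ends with "metastasis site information, laboratory values, if available, survival status". Neither section lists a date of registration, death or last contact. Section 9.9 names only too few patients as a limitation, and Annex 1 lists no stand-alone document that could supply the missing rules.

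**The concern.** A patient who starts sunitinib, and is invited into the registry some months later, must have survived those months to be invited. Patients who started at the same time and died first never appear. If survival is timed from sunitinib start, the time between start and registration is free of deaths by design. Ordinary Kaplan-Meier nevertheless counts it as time at risk, which enlarges the early risk sets and pushes the curve up.

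For overall survival the error runs in one direction. The contrast between risk groups can be distorted either way, because the selection acts differently on groups with short and long survival. The plan as written would also not reveal the problem. Starts before March 2019 can be recognised from the starting date, but the lag between start and registration cannot be computed without the registration date.

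**Working it through.** **The plan's own figures.** The plan states no survival figure, event count or power. Its only number is about 400 patients, a feasibility estimate. It cannot be rebuilt from the volumes quoted with it: 250 × 44/12 ≈ 917 and 100 × 6 × 44/12 = 2,200, so 400 would need an eligible share of 44% or 18%, and neither is stated. The point here does not depend on it.

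**Inputs from the documents.** Registration runs from March 2019 to October 2022, 44 months (9.2). Data collection starts on 9 January 2023 (section 6), so follow-up is cut 46.5 months after the registry opened.

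**Assumptions.** Survival from sunitinib start is exponential with a true median of 24 months, S(t) = 2^(−t/24). Patients are registered only while alive. The lag patterns below are also assumed.

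**Hand check.** Let a share f = 25% of the registered cohort enter exactly 12 months after start, the rest at start, with no censoring.
- Up to month 12 the naive curve is (1 − f)·S(t) + f. At 12 months this is 0.75 × 0.707 + 0.25 = 0.780, against a true 0.707.
- After month 12 it falls at the true rate. The naive median solves 0.780 × 2^(−(t−12)/24) = 0.5, so t = 12 + 24 × log₂(1.561) = 12 + 15.4 = 27.4 months.

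**Simulation.** Each scenario had 400,000 sunitinib starts. Starts were uniform from b months before opening to month 44. Registration was at the later of start plus lag and registry opening. Patients were kept if alive at registration and registered by month 44. Medians in months:

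| Scenario | Ordinary Kaplan-Meier | Entry at registration |
|---|---|---|
| All registered at start | 24.0 | about 24 |
| Starts reaching back 12 / 24 / 36 months | 25.2 / 27.9 / 31.3 | about 24 |
| Exponential lag, mean 1 / 3 / 6 months | 25.0 / 26.7 / 28.8 | about 24 |
| Back 24 months plus mean lag 3 | 30.0 | about 24 |

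In the last scenario, using only the starting date and the opening of the registry leaves a median of 26.7. The registration date is needed to remove the rest.

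**A second entry model.** A fixed share of registered patients enters uniformly over a period after start (true median again 24). Naive medians are 25.8 (25% over 0–12 months), 28.1 (25% over 0–24), 27.4 (50% over 0–12) and 31.6 (50% over 0–24). A true 24-month survival of 50.0% is estimated as 52.6% to 62.3%. For true medians of 18 to 30 months the overstatement is about 1.7 to 7.9 months. Entry at registration recovers the true median within 0.1 month.

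**Against sampling error.** In 1,500 replicates of 400 patients with no late entry, 95% of estimated medians fall between 20.3 and 28.6 months.

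**Response rate.** With a responder death hazard ratio of 0.4 (assumed), a true 30% becomes 30.5% to 32.4%.

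**Risk groups.** With assumed true medians of 8 and 40 months (gap 32, ratio 5.0), a 36-month look-back gives about 9.9 and 48.3 (gap 38, ratio 4.9). A 6-month mean lag gives about 12.0 and 45.2 (gap 33, ratio 3.8).

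**The case against.** The strongest reply is that the registry protocol, which is not among the documents, decides when patients are registered. If it requires registration at or before first-line start, or allows deceased patients to be entered retrospectively, the bias is absent or smaller. Three conditions must hold together: late registration, registration only while alive, and timing from sunitinib start. The second is inferred from the word for invitation, and section 9.7 names no origin at all. Timing from registration would avoid the bias, although it would no longer measure survival from treatment start. This stands, and it is why the conclusion is conditional.

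The sizes are assumed, and the upper end is generous: with a 36-month look-back, about 34% of the cohort started before March 2019, a share the documents do not support. Four of the six single-mechanism scenarios lie inside the no-bias sampling range. The 6-month lag leaves it by only about 0.2 month (28.8 against 28.6). This also stands, but sampling error is reported with the estimate and shrinks with more patients, whereas this bias does neither.

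The primary objective, response by risk group, is little affected, and survival is a secondary, descriptive objective. That limits the weight of the point.

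Finally, the missing time origin and the missing death and last-contact dates are gaps in their own right, and survival status might be a heading that covers dates. Even so, nothing listed suggests a registration date, and without it nobody could later tell a bias of zero from one of several months.

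**Conclusion.** The concern holds as a conditional one. The plan permits entry after sunitinib start, specifies nothing to handle it, and does not extract the date needed to detect or correct it. If late entry occurred among living patients and survival is timed from sunitinib start, overall survival is overstated. With an assumed true median of 24 months, the single-mechanism scenarios (look-back or lag alone) give about 1 month in the mildest cases, well within sampling error at 400 patients, and about 5 to 7 months in the largest, beyond it. The bias is zero if all patients registered at sunitinib start. The effect on response rate is likely small, and the effect on survival differences between risk groups has no fixed direction. The change should be made because it is cheap and settles the question, but it does not threaten the primary objective.

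**What to change.** - **Sections 9.3 and 9.6:** add the registration date and the dates of death and last contact, or each as days from sunitinib start, which suits anonymised transfer.
- **Section 9.7:** name sunitinib start as the time origin. Use Kaplan-Meier and group comparisons that allow delayed entry (left truncation), with each patient joining the risk set at registration. Tabulate the lag from start to registration by risk group.
- **Sensitivity analysis:** repeat survival and response rate in patients who started sunitinib at registration or within a short, pre-stated window of it. The response part also needs a response variable, which 9.3 and 9.6 do not list.
- **Section 9.9:** name late entry as a limitation.

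The cost is three dates or intervals per patient, some analysis code, and possibly software other than SPSS 19.0. Some precision is lost in the lag scenarios: with a 6-month mean lag and 400 patients, the standard deviation of the median is 2.4 against 2.2 months. With a 1-month window, the sensitivity analysis would keep about 270 to 330 of 400 patients in the look-back scenarios and about 80 to 260 in the lag scenarios. The survival estimate may be less favourable. The request is best made before extraction, because only the listed variables are transferred for analysis.

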9.2.1. Inclusion criteria

Data record in registry must meet all of the following inclusion criteria to be eligible for inclusion in the study:

1. Being a Turkish citizen
2. Being older than 18 years-old

3. Being clinically diagnosed and treated with mRCC
4. Being treated with Sunitinib in first line

9.2.2. Exclusion criteria

Data record in registry meeting any of the following criteria will not be included in the study:

1. Patients whose treatment was initiated but excluded from follow-up for any reason.

9.3. Variables

The following variables will be extracted from RCC Registry in the scope of this study:

- Demographic information (age, sex)
- Physical measurements (height and weight measurements)
- Disease and concomitant disease history (Hypertension, Diabetes mellitus)
- Previous treatments (ACE-I / ARB, statin)
- Age of start of Sunitinib,
- Smoking history,
- Date of diagnosis
- Surgery type (Radical nephrectomy, partial nephrectomy)
- Histopathological information
 - Pathological type,
 - Pathological stage and location,
 - T size and location
 - Fuhrman Grade,
 - Adrenal involvement,
 - Lymph node (LN) involvement,
 - Number of LNs removed,
 - Sarcomatoid feature,

- Other involvement information
- Treatment given (order of treatment given, starting date, dose, dose changes, if available)
- Discontinuation of treatment information and the reason
- Previous IFN use
- Toxicities leading dose reduction and treatment discontinuation
- Information of risk (International Metastatic RCC Database Consortium (IMDC), Memorial Sloan Kettering Cancer Center (MSKCC) subgroups)
- Performance scores (ECOG)
- Metastasis site information
- Laboratory values, if available
- Survival status

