4. ABSTRACT

A Retrospective Registry Based Study for Evaluating Treatment Response in Patients Targeted Treated with Metastatic Renal Cell Carcinoma (mRCC) with Sunitinib in First-line Therapy, dated 18 November 2022 and with version number of 3.0.

Objectives:

The aim of this study is to observe the treatment response in patients with mRCC targeted treated with Sunitinib in first-line therapy.

Primary Objective:

- Evaluation of Sunitinib treatment responses/objective response rate according to disease risk group in patients with mRCC targeted treated with Sunitinib in first-line therapy in Turkey

Secondary Objectives:

- Evaluation of survival and treatment response to Sunitinib treatment regimen
- Determination of factors affecting the treatment regimen change and the frequency of these factors in patients with mRCC
- Determination of demographic, clinical and pathological characteristics of patients with mRCC
- Determination of median duration use of patients using IFN.

This is a non-interventional, retrospective, evaluational study, based on data extracted and analyzed from the RCC Registry.

This study was designed to answer the Sunitinib treatment responses/objective response rate according to disease risk group in patients with mRCC.

All patient data in the RCC Registry, meeting all of the inclusion criteria will be included in the study.

The variables to be obtained from this study:

- Demographic information (age, sex)
- Physical measurements (height and weight measurements)
- Disease and concomitant disease history (Hypertension, Diabetes mellitus)
- Previous treatments (Angiotensin Converting Enzyme Inhibitor (ACE-I) / Angiotensin Receptor Blockers (ARB), statin)
- Age of start of Sunitinib,
- Smoking history,
- Date of diagnosis
- Surgery type (Radical nephrectomy, partial nephrectomy)

PFIZER CONFIDENTIAL

- Histopathological information
 - Pathological type,
 - Pathological stage and location,
 - T size and location
 - Fuhrman Grade,
 - Adrenal involvement,
 - Lymph node (LN) involvement,
 - Number of LNs removed,
 - Sarcomatoid feature,
- Other involvement information
- Treatment given (order of treatment given, starting date, dose, dose changes, if available)
- Discontinuation of treatment information and the reason
- Previous IFN use
- Toxicities leading dose reduction and treatment discontinuation

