8. RESEARCH QUESTION AND OBJECTIVES

The purpose of this study is to observe the treatment response in patients with mRCC treated with Sunitinib in first-line therapy.

Primary Objective:

- Evaluation of Sunitinib treatment responses/objective response rate according to disease risk group in patients with mRCC treated with Sunitinib in first-line therapy in Turkey

Secondary Objectives:

- Evaluation of survival and treatment response to Sunitinib treatment regimen
- Determination of factors affecting the treatment regimen change and the frequency of these factors in patients with mRCC
- Determination of demographic, clinical and pathological characteristics of patients with mRCC
- Determination of median duration use of patients using IFN.

[figure not shown]

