9.4. Data sources

RCC Registry will be used as the sole data source for this study.

For this purpose, no Case Report Forms (CRFs) or Data Collection Tools (DCTs) will be utilized, but the RCC Registry database will be used directly. Eligible patients' data will be anonymized and extracted for analysis by the registry owner, for this study.

The RCC Registry was approved by Ankara University Ethical Committee in October 2018 and by Ministry of Health in March 2019.

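### The primary objective is response rate by risk group, but none of the three extraction lists names a tumour-response variable

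*Combined protocol and SAP*

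**What the plan says.** **Objectives.** Section 8 gives the primary objective as "Evaluation of Sunitinib treatment responses/objective response rate according to disease risk group". The first of the four secondary objectives is "Evaluation of survival and treatment response to Sunitinib treatment regimen". Section 9.1 repeats the purpose: "This study was designed to answer the Sunitinib treatment responses/objective response rate according to disease risk group in patients with mRCC".

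**Variables.** Three places list what is to be taken from the registry:
- The abstract, under "The variables to be obtained from this study".
- Section 9.3, under "The following variables will be extracted from RCC Registry in the scope of this study".
- Section 9.6, under "The below data in Registry database will be anonymized by registry administrators". It then states "This anonymized data will be transferred to the clinical database of the study in Omega CRO".

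All three include the IMDC and MSKCC risk subgroups, and all three end with survival status.

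**Source.** Section 9.4 makes the registry the sole source and says that "no Case Report Forms (CRFs) or Data Collection Tools (DCTs) will be utilized". Annex 1 lists no stand-alone documents.

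**The concern.** An objective response rate by risk group needs two things for each patient: the risk group and a response category. The lists ask for the first and not the second. They go down to statin use, smoking history and the number of lymph nodes removed, so brevity does not explain the absence of the primary outcome.

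An export that follows the lists would leave the CRO with risk groups and nothing to tabulate against them. The primary objective could not be answered, nor could the response part of the first secondary objective. No other data stream in the plan could fill the gap.

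**Working it through.** There is no plan figure to reproduce. The check compares the objectives with the lists, item by item.

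**1. Count the entries and look for response.**

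| Place | Headings | Histopathology sub-items | Total | Naming risk group | Naming response, criteria or assessment date |
|---|---|---|---|---|---|
| Abstract | 19 | 8 | 27 | 1 | 0 |
| 9.3 | 19 | 8 | 27 | 1 | 0 |
| 9.6 | 19 | not repeated | 19 | 1 | 0 |

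A text search of the lists for response, RECIST, progression, lesion, ORR, imaging, radiology and target found none of them. This is essentially one list given three times, so the evidence is one omission repeated consistently, not three independent ones.

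**2. Could a listed item stand in for response?**
- Treatment given is itemised as order, start date, dose and dose changes. It carries no outcome.
- Reason for discontinuation may record progression. It cannot separate complete response, partial response and stable disease, so it gives no numerator for a response rate.
- Tumour size, metastasis sites and other involvement describe pathology or extent of disease, not change on treatment.
- Survival status bears on survival, not response.

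**3. Does other methods text ask for the field?** Section 9.1 names response as the purpose but requests no data item. The word does not occur from 9.2 to 9.10. Section 9.7 describes no response analysis. The lists contain no redaction or missing figure.

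**4. Objectives affected.** Primary (1) + first secondary (1) = 2 of 5.

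**5. Time for a late repair (section 6 dates).**
- Extraction, 9 January to 13 February 2023: 22 + 13 = 35 days.
- End of extraction to final report on 1 April 2023: 15 + 31 + 1 = 47 days.

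**The case against.** The strongest reply is that some wording is broader than the lists. The abstract speaks of including all registry patient data that meet the inclusion criteria, 9.4 says the database is used directly, and 9.8 speaks of extracting eligible records. No list says that it is exhaustive. On that reading whole records are in scope, and the lists only name content groups. Read in context, though, these sentences say which patients and which source are used, not which fields. Section 9.6 does speak to fields, and it ties the transfer to its own list.

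A second reply is that nobody would run a response study without noticing that response was missing, and that 9.8 provides for reconciliation with the registry. That could repair the gap if the registry holds the field. But the route is triggered by problems of protocol compliance or adverse events, and an export without response would match the lists. The sponsor receives no individual patient data under 9.6, so it could not see the missing column in the dataset itself.

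What stands is that the consequence is conditional. The protocol does not show that the registry lacks response data. It shows only that the plan does not ask for them.

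**Conclusion.** The point holds and must be fixed before extraction. Confidence is high that response is missing from all three lists. The consequence rests on one assumption, that the lists are applied as written. In that case response is absent for all of the approximately 400 planned patients, and two of the five objectives cannot be met in whole or in part.

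A separate and less certain point: 9.7 plans Kaplan-Meier estimates, while the lists give only survival status, which may or may not carry a date. That needs clarification and is not part of this verdict.

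**What to change.** 1. Before the extraction planned for 9 January 2023, ask the registry owner whether tumour response is recorded, by which criteria and with what dates.
2. If it is, add three fields to the abstract, 9.3 and 9.6: best overall response (complete response, partial response, stable disease, progressive disease, not evaluated), the criteria used, and the assessment date. Best overall response is a suggested form; the protocol itself specifies none.
3. In 9.7, define the objective response rate, say how patients without an evaluation are counted, and describe the tabulation by risk group. Without this, the new columns supply data but no analysis.
4. If response is not recorded, restate the primary objective and the response part of the first secondary objective.
5. As a clarification, state whether survival status includes the date of death or last contact, and add the progression date if progression-free survival is intended.

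If the registry holds the data, the cost is three export columns, the same short edit in three places and a few sentences in 9.7. If it does not, the cost is larger, because the study's main question has to change. That is better known before extraction than in the 47 days between its end and the final report.

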[figure not shown]
[figure not shown]

Study information

Title	A Retrospective Registry Based Study for Evaluating Treatment Response in Patients Targeted Treated with Metastatic Renal Cell Carcinoma (mRCC) with Sunitinib in First-line Therapy
Protocol number	A6181235
Protocol version identifier	3.0
Date	18 November 2022
Active substance	Sunitinib
Research question and objectives	
Primary Objective:
 
• Evaluation of Sunitinib treatment responses/objective response rate according to disease risk group in patients with mRCC targeted treated with Sunitinib in first-line therapy in Turkey 
Secondary Objectives:
 
• Evaluation of survival and treatment response to Sunitinib treatment regimen,• Determination of factors affecting the treatment regimen change and the frequency of these factors in patients with mRCC• Determination of demographic, clinical and pathological characteristics of patients with mRCC• Determination of median duration use of patients using interferon (IFN)

PFIZER CONFIDENTIAL

Author	Assoc. [name] [REDACTED]
Co-author	PPD [REDACTED]

This document contains confidential information belonging to Pfizer. Except as otherwise agreed to in writing, by accepting or reviewing this document, you agree to hold this information in confidence and not copy or disclose it to others (except where required by applicable law) or use it for unauthorized purposes. In the event of any actual or suspected breach of this obligation, Pfizer must be promptly notified.

PFIZER CONFIDENTIAL

[figure not shown]
[REDACTED]

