6. MILESTONES

Milestone	Planned date
Start of data collection	9 January 2023
End of data collection	13 February 2023
Final study report	01 April 2023

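### Can the median duration of IFN use be obtained when no IFN stop date is listed and eligibility after IFN is not spelled out?

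*Combined protocol and SAP*

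**What the plan says.** The last of the four secondary objectives in Section 8 is "Determination of median duration use of patients using IFN"; the Study information page and the abstract carry it too. The variable list appears in the abstract, in Section 9.3 and in Section 9.6. In each, the one IFN-specific item is "Previous IFN use". Two neighbouring items are not tied to a drug. One is "Treatment given (order of treatment given, starting date, dose, dose changes, if available"), and the other covers information on stopping treatment together with the reason. Section 9.4 makes the registry the sole source, used directly and without case report forms.

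The population is worded in two ways. The title has "Patients Targeted Treated with Metastatic Renal Cell Carcinoma (mRCC) with Sunitinib in First-line Therapy" and the abstract has "The aim of this study is to observe the treatment response in patients with mRCC targeted treated with Sunitinib in first-line therapy". Section 8 has "The purpose of this study is to observe the treatment response in patients with mRCC treated with Sunitinib in first-line therapy", and inclusion criterion 4 in Section 9.2.1 reads "Being treated with Sunitinib in first line". The word targeted is not defined anywhere.

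**The concern.** A duration has to come from a start and a stop date or from a recorded length, and the lists name neither a stop date nor a length for IFN. The registry owner extracts and anonymises the records before they reach the CRO, so a missing field would mean a second request. Data collection is planned to end on "13 February 2023", with the report due on 1 April 2023.

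The wording of the population adds to the doubt. With targeted, the phrase can mean the first targeted agent, which would leave room for earlier IFN. Without it, first line can be read as first systemic treatment, which would remove patients given IFN for metastatic disease before sunitinib. That reading could leave few or no patients for the IFN objective. It would also change who enters the cohort used for every other objective, including the primary one.

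**Working it through.** No formula or stated figure is at issue. The check compares the texts and the calendar.

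1. **What is named.** Section 9.3 has 19 top-level items. Two name a date: diagnosis, and treatment start within the treatment item. None names a treatment stop date or an IFN duration. The gap in the wording is real.

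2. **What the headings can hold.** The treatment item covers order of treatment and starting date for treatments in general. The discontinuation item lists information on stopping separately from the reason, so a stop date fits there naturally. If the registry logs IFN as a treatment, these two items give its duration. The IFN item could also hold a recorded length, and one such field would be enough. The documents neither confirm nor rule out any of this.

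3. **Whether the analysis rule works.** Section 9.7 summarises non-normal numerical variables by median and interquartile range, and the objective asks for a median. No further rule is needed once the duration is in hand.

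4. **Whether prior IFN is compatible with eligibility.** There are 4 inclusion criteria and 1 exclusion criterion, 5 in all, and none mentions IFN. An IFN objective and an IFN history item make little sense if such records were meant to be kept out. The reading that fits all the sections is that prior IFN does not by itself disqualify a record. The setting in which IFN was given is not stated, so the conflict with a strict reading of first line is itself an inference.

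5. **Time available.** Version 3.0 is dated 18 November 2022 and data collection starts on 9 January 2023: 12 + 31 + 9 = 52 days. The Section 9.2 schedule gives November and December 2022 to preparation and approvals. Collection then runs 22 + 13 = 35 days to 13 February, and 15 + 31 + 1 = 47 days remain to the report. Counting only the 35 and 47 days would leave out the period in which an extraction request is normally drawn up.

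**The case for a change.** The best argument for a change is a dilemma. If IFN is logged as a treatment with its order, then sunitinib after IFN is not literally first, and criterion 4 is in doubt. If IFN is not logged that way, only an undated history item remains. The Section 9.8 safeguard may not help either. It is triggered by problems of protocol compliance or adverse events, and an extract without an IFN stop date still complies with the list. The remedy would also be cheap: name the dates or a duration in three copies of the list and settle one population wording.

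Part of this stands. The documents do not say how the registry codes IFN, and Section 9.8 is only a partial safeguard. But the first branch assumes that the registry's treatment order is the same thing as the protocol's first line, which no section says. The second assumes that the IFN item is a bare yes or no, which is not stated either. An analyst with an IFN-duration objective and no duration would see the gap on trying to produce that table, whatever triggers the formal check. A low cost is not in itself a reason to amend when no stated rule is shown to give a wrong result. The contrast over targeted is also thin: the title is awkward English, and nothing links the word to IFN.

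**Conclusion.** The observation about the text is correct, but it does not call for a change. It is missing detail that the registry owner and the CRO can be expected to supply when they agree the extract, together with an uneven population wording that the rest of the protocol resolves. At most, one of four secondary objectives is touched, and it is descriptive. The size and direction of any effect on the primary response rate, among the roughly 400 patients planned, cannot be derived, because the documents give no figure for IFN use.

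This rests on two assumptions: that the registry holds IFN dates or a duration under its treatment, discontinuation or IFN items, and that records with prior IFN are meant to be eligible, as the objective and the IFN item imply. If the registry turned out to hold no such data, that one objective could not be reported as worded. The response and survival objectives do not require an IFN duration.
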